# Randomisation and Blinding/Allocation Concealment

The randomisation process will be set up and tested by the trial statistician. Participants will be randomly allocated (using computer generated random numbers) to the intervention or control group, in a 1:1 ratio stratified by location. The aim is to recruit 28 participants at each of the three locations. Within each location, participants will be randomised in two batches of 14, with seven participants allocated to each trial arm per batch. The seven participants in the intervention arm of a given batch will form the group within which they undertake the intervention. As part of this pilot RCT, one key objective is to assess the speed of recruitment. The maximum time we are willing to wait to recruit 14 participants per batch will be reviewed and discussed in team meetings. Currently, it has been decided that a batch will proceed with no fewer than twelve participants (assuming two could drop out, leaving four in an intervention group). However, the specific time frame for reaching this minimum threshold has yet to be determined.

For each batch, the trial manager will provide the statistician with a list of unique, non-identifying participant numbers to maintain allocation concealment. The statistician will then match these numbers to the pre-generated allocation sequence and relay the assigned allocations back to the trial manager. The trial statistician and health economist will remain formally blinded to group allocation until the analysis begins.

Other members of the research team will not be formally blinded, as they may need to access participant data or may inadvertently learn group allocations. For example, green providers may report participant engagement using names (since they lack access to participant identifiers), such as noting if a participant spends intervention sessions on their phone rather than engaging in activities. Additionally, if participants contact the research team to enquire about their group allocation, their names will be recognised alongside their assigned group.

To maintain confidentiality, names, contact details, and participant identifiers will be stored separately and held by the trial manager. Access to these details will be granted only when necessary, such as in cases where a participant poses a risk to themselves or others and needs to be withdrawn from the trial.

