#### Nature-based Providers

Through learning from the feasibility stage, we better understand the challenges of provider participation. Initial workshops led by the research team will be used to support the groups to map their planned activities to the handbook mechanisms, ensure appropriate staff training and staff are in place, and provide details on the research being undertaken. Capacity issues mean that the providers may not be able to deliver more than one course at a time, and that there may be staff turnover, requiring additional input from the research team to ensure new members understand the expectations of the research project. We have allowed eight months for the providers to run up to three six-week courses with approximately 27 participants in series. The viability of this will be assessed in order to inform the full trial in the future.

The meaningful and committed involvement of nature-based providers throughout the project represents significant investment of time and can affect capacity for their day-to-day activities. Therefore, they will be supported by an initial engagement payment which will enable them to participate in training, delivery refinement workshops, administration associated with recruitment and so on.

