# Sample size and Power Calculations

As this is a pilot trial a formal sample size calculation for evaluating the impact of the intervention on the outcomes is not appropriate. This pilot RCT will enable us to identify the most appropriate primary outcome (through assessing completeness of data provided, score variability, and participant feedback on completing the questionnaire) and sample size for a future full trial. Based on published recommendations for pilot RCT size of 70 (35 per arm) (Tearle et al 2014) we will aim to recruit 84 participants, allowing for 20% drop out up to T1. Each site will aim to run up to three courses, each accommodating 7–10 participants. The minimum required number of participants per course is four. A total of eight groups with at least four participants each provides sufficient sample size to estimate a dropout rate of 15%, with a 95% confidence interval ranging from 8% to 24%.

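### The 8% to 24% interval for a 15% dropout rate does not follow from eight groups of at least four; it fits the whole sample of 84

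*Protocol*

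**What the plan says.** The sample size section sets the target at 84, starting from a published recommendation of 70 for pilot trials and allowing for 20% dropout up to T1. It then describes delivery: "Each site will aim to run up to three courses, each accommodating 7–10 participants", and "The minimum required number of participants per course is four". The precision claim follows: "A total of eight groups with at least four participants each provides sufficient sample size to estimate a dropout rate of 15" per cent, "with a 95% confidence interval ranging from 8% to 24" per cent. No interval method is named.

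Two other sections bear on the number of groups:

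- Randomisation and Blinding/Allocation Concealment plans 28 participants at each of three locations: "Within each location, participants will be randomised in two batches of 14, with seven participants allocated to each trial arm per batch". The intervention half of each batch is the group that attends together.
- Nature-based Providers allows each provider "up to three six-week courses with approximately 27 participants in series".

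Under Main Objectives, the primary objective is recruitment and retention in the intervention and control arms.

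**The concern.** The sentence presents a floor, eight groups of four, as sufficient for a stated precision. That floor is 32 people, fewer than half of the 84 to be recruited, and an interval only 16 points wide around 15% looked too narrow for it. The number eight also matches neither the batches in the randomisation section nor the maximum number of courses.

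This is the only numerical precision statement in the Protocol, and it concerns dropout, which is the reverse of the retention rate in the primary objective. A steering committee that took it at face value could believe that recruitment falling towards 32 would still deliver 8% to 24%. The number of groups matters a second time, because the Planned Data Analysis section treats each intervention group as a cluster in the mixed model and applies a small-sample degrees-of-freedom correction for that reason.

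**Working it through.** **Inputs, all from the Protocol.** Dropout 15%, limits 8% and 24%, eight groups, at least four per group (Sample size and Power Calculations); 84 recruited, 42 per arm (Recruitment and Participant Identification); three locations, two batches each, seven per arm per batch (Randomisation and Blinding/Allocation Concealment); up to three courses per site (Sample size and Power Calculations; Nature-based Providers).

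**Formula.** Exact (Clopper-Pearson) limits for x dropouts among n, with x = 0.15n:

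- lower = 2.5th percentile of Beta(x, n − x + 1)
- upper = 97.5th percentile of Beta(x + 1, n − x)

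**Step 1: reproduce the printed interval.** With n = 84, x = 12.6 and the exact limits are 8.1% and 24.46%, which round to 8% and 24%. A search over n from 15 to 199 at a rate of exactly 15% finds limits that round to 8% and 24% only for n = 84 to 94 (exact) or n = 73 to 80 (Jeffreys). Wald, Wilson and Agresti-Coull give that pair at no n.

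**Step 2: the stated basis.** 8 × 4 = 32, so x = 4.8.

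| Method at n = 32 | 95% limits |
|---|---|
| Exact | 4.9% to 32.0% |
| Wilson | 6.5% to 31.0% |
| Agresti-Coull | 6.0% to 31.5% |
| Jeffreys | 5.8% to 30.1% |
| Wald | 2.6% to 27.4% |

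None gives 8% to 24%. The exact width is 32.0 − 4.9 = 27.1 points, against 24 − 8 = 16 stated.

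**Step 3: more generous readings of eight groups.**

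| Reading | n | Exact 95% limits |
|---|---|---|
| Eight groups that start with six (half of the minimum batch of twelve) | 48 | 6.3% to 28.3% |
| Eight groups of the planned seven | 56 | 6.9% to 27.1% |
| Eight groups of four plus as many controls | 64 | 7.3% to 26.1% |
| Eight courses at the upper capacity of ten | 80 | 8.0% to 24.7% |

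The first three miss under all five methods. The last rounds to 8% and 24% only under Jeffreys (8.5% to 24.0%), and 80 people in the intervention arm is not possible with 42 planned.

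**Step 4: one arm.** With n = 42, x = 6.3 and the exact limits are 5.9% and 29.4%.

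**Step 5: the group count.** Planned intervention groups: 3 locations × 2 batches = 6, and 6 × 7 = 42, which agrees with the arm size. Course ceiling: 3 sites × 3 = 9. The figure eight appears only in the precision sentence and is derived from neither.

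**The case against.** The best defence is that the printed interval is right for the trial as planned: it is the exact interval for 15% of 84, and 84 is the recruitment target. That stands. The error lies in the basis given for the interval, not in the interval itself.

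A second defence is that four is a floor and the planned group size is seven. The randomisation section even describes four as what would be left after two losses, so 32 may not be the intended denominator. This softens the contrast of 27 points with 16, but does not rescue the sentence: it claims the precision at the floor, and 48, 56 and 64 miss as well.

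Some stronger conclusions are tempting and are not supported:

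- *That eight groups are impossible.* Three courses per site is a ceiling, so 3 + 3 + 2 = 8 courses is allowed. Courses and randomised intervention groups may also be different units: controls are offered the programme after T2, and about 27 participants per provider is close to a location's 28 across both arms. Six is itself a target, since a batch may proceed with twelve, and 84 / 12 = 7 batches. What can be said is that eight is not derived and does not match the six groups of the planned randomisation.
- *That the interval can only have come from 84.* No method is named, and Jeffreys at 12/80 also rounds to it. The nearest whole counts at 84 give 7.6% to 23.6% (12 dropouts) and 8.5% to 25.0% (13), so the match at 84 uses the fractional 12.6.
- *That the missing one-arm interval is part of the arithmetic error.* The sentence speaks of one dropout rate, without arms. A one-arm figure is a useful addition because the primary objective names both arms.

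Finally, the target of 84 rests on the published recommendation and its inflation, not on this sentence, and the analysis section will report the intervals actually achieved.

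**Conclusion.** The sentence is wrong as written. Eight groups of at least four guarantee 32 people, and at 32 a 15% dropout rate carries an exact interval of about 5% to 32%. The printed 8% to 24% needs roughly 73 or more participants at a rate of 15% and agrees with the exact interval for all 84. The number eight has no derivation in the Protocol.

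These intervals treat dropouts as independent. If dropout is correlated within groups they widen. With an intracluster correlation of 0.05, which is an assumption because the Protocol gives none, eight groups of four have an effective size of 32 / (1 + 3 × 0.05) = 27.8 and an exact interval of about 4% to 34%. At 0.01 and 0.10 the effective sizes are 31.1 and 24.6. The conclusion does not depend on this.

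The consequence is limited to how the precision for retention is described. Neither the recruitment target nor the planned analysis is affected.

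**What to change.** 1. Replace the precision sentence with, for example: With 84 randomised, an overall dropout of 15% is estimated with an exact 95% confidence interval of about 8% to 24%; within one arm (n = 42) the interval is about 6% to 29%. This also names the method.
2. Delete the justification by eight groups of four.
3. Reconcile the number of intervention groups and of courses across Sample size and Power Calculations, Randomisation and Blinding/Allocation Concealment, and Nature-based Providers. Say whether the three courses per site include wait-list delivery.

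The cost is Protocol wording. The one-arm figure is less favourable than the one now printed. No extra participants are needed.

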# Planned Data Analysis

# Quantitative Data

A full statistical analysis plan will be specified and signed off in advance of data lock.

A CONSORT diagram will be used to describe the participant flow through the trial, with counts and percentages of those recruited and retained in the study (Eldridge et al 2016).

Characteristics related to feasibility of the trial will be reported with 95% confidence intervals, including: the percentage of screened people that are eligible, the percentage of screened people that are recruited, the number of people recruited per location per week, the percentage of participants that provide follow-up data, the percentage of intervention arm participants that attend at least 4 of the 6 nature-based sessions and the percentage of participants that complete each outcome measure. Characteristics of the study participants will be summarised using means and standard deviations (or medians and interquartile ranges) for continuous variables, and numbers and percentages for categorical variables.

As this is a pilot study, estimating intervention effectiveness is not a key objective. However, its potential impact on the mental health and wellbeing outcomes at follow-up will be estimated. Trial arms will be compared using mixed ("multilevel") linear regression models. These models will account for the correlation between the responses of intervention arm participants within the group (cluster). Satterthwaite's degrees of freedom correction will be applied to account for the small number of clusters in the analysis. If there are convergence problems, ordinary linear regression models will be fitted instead. The comparisons will be adjusted for the baseline score of the outcome. Adjusted mean differences between the trial arms and two-sided 95% confidence intervals will be reported; no hypotheses testing will be undertaken. No subgroup analyses will be undertaken.

To calculate intervention costs, the resource used for training and delivering the intervention (preparation, delivery, travel time) will be collected from the trainers and service managers, and nationally applicable unit costs will be applied.

To explore barriers and facilitators to attendance, data collection forms will be designed to allow linkage of attendance data to participants' home postcodes and Index of Multiple Deprivation (IMD) using a participants' unique identifier code. This data linkage will enable us to investigate whether travel costs and/or residence in an area with relative high social deprivation is correlated to participant attendance using the Pearson correlation coefficient. Travel time and mileage from a participant's home postcode to the intervention site will be calculated using Google Maps to incorporate participant travel costs, based on HMRC reimbursement rates (https://www.gov.uk/government/publications/rates-and-allowances-travel-mileage-and-fuel-allowances/travel-mileage-and-fuel-rates-and-allowances).

Data collection methods for primary, secondary and social care resource use, as well as personally incurred expenses (e.g. travel, counselling), informal care/support and workforce participation will also be piloted. These data will be collected from participants using a bespoke resource use questionnaire (www.Dirum.org) and reviewed by PPI members. Responses to the resource use questionnaire will indicate whether participants have difficulties understanding or completing the questions. The potential of the group-based intervention to improve wellbeing during the trial will be measured using ONS4. Additionally, SWEMWBS will be used to calculate

a Mental Well-being Adjusted Life Years (MWALYs) using the preference-based, UK tariff derived from members of the general public (Yiu et al., 2023).

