# Methods

This is an external pilot RCT of group, nature-based activities for people with mild-to-moderate depression and/or anxiety. We aim to recruit 84 people via GPs, community groups and social media advertising who, following screening for mild-to-moderate depression and/or anxiety, will be randomised to receive either a 6-week nature-based activity course at one of three locations in the south west of England, together with usual care, or receive usual care alone. Randomisation will be stratified by location. We will collect data on participants' mental health and wellbeing using the Office of National Statistics "Personal Wellbeing" (ONS4); the short version of the Warwick–Edinburgh Mental Wellbeing Scale (sWEMWBS); the Patient Health Questionnaire (PHQ-9); General Anxiety Disorder measure (GAD-7); and the Three-Item Loneliness Scale. These assessments will be administered prior to the randomisation and at 6 and 12 weeks after intervention start (or equivalently at approximately 8- and 14-weeks post-randomisation). Data will be collected online using a secure service. Health service use data will also be collected. We will use decliner and participant surveys to understand factors that affect participation and focus group discussions to understand the experiences of those participating in the pilot to help refine the process for the future trial.

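### The outcome model leaves out location, the stratification factor, so if sites differ the confidence interval for the arm difference can be wider than the design warrants

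*Protocol*

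**What the plan says.** **Design.** Protocol, Methods (Trial Overview): "Randomisation will be stratified by location". Trial Design repeats that individuals are allocated 1:1 within each of the three locations, and Randomisation and Blinding/Allocation Concealment has allocation "in a 1:1 ratio stratified by location". That section adds: "Within each location, participants will be randomised in two batches of 14, with seven participants allocated to each trial arm per batch". It then defines the cluster: "The seven participants in the intervention arm of a given batch will form the group within which they undertake the intervention".

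**Analysis.** Planned Data Analysis (Quantitative Data) compares arms with mixed linear models that allow for correlation among intervention-arm participants in the same group. Small numbers are handled as follows: "Satterthwaite's degrees of freedom correction will be applied to account for the small number of clusters in the analysis". There is a fallback: "If there are convergence problems, ordinary linear regression models will be fitted instead". On covariates it says: "The comparisons will be adjusted for the baseline score of the outcome". Results are adjusted mean differences with two-sided 95% confidence intervals and no hypothesis tests. A full statistical analysis plan is to follow before data lock.

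Location is not named as a fixed or random term in either model.

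**The concern.** The protocol states the covariate, the random-effect structure, the degrees-of-freedom method and the fallback, but omits the one factor on which it stratified. As written, the analysis does not follow the randomisation.

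This matters because of nesting. The only between-participant structure in the model is the intervention group, and the groups sit two to a location. A site difference shared by both arms drops out of the arm comparison by design. The model does not know that. In the intervention arm it reads part of the difference as variation between groups. In the control arm, which has no group effect, the difference goes into the residual. The standard error for the arm difference is then too large.

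Two outputs are exposed. One is the width of the interval for potential effectiveness, a listed secondary objective. The other is any group variance or ICC taken from this model to plan the definitive trial.

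**Working it through.** The documents give no between-site variance, ICC or interval width, so there is no stated figure to reproduce. The check takes the structure from the protocol and varies the missing quantities.

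**Inputs from the protocol.** 3 locations × 2 batches × 7 per arm = 42 per arm, in 6 intervention groups, 2 per location. The model has a group effect in the intervention arm only, a baseline covariate, Satterthwaite degrees of freedom and a two-sided 95% interval.

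**Assumptions.** Site share of the variance left after baseline adjustment: 0, 2, 5, 10 or 20%. Group ICC: 0 or 5%. Analysed: 6 per arm per batch, so 3 × 2 × 2 × 6 = 72, with equal retention in both arms.

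**Step 1: how much site variance reaches the group term.** Let σ² be the residual between-site variance. Without a location term, the 6 group means vary about one mean on 5 degrees of freedom. The expected sum of squares due to sites is 2 groups per site × (3 − 1) × σ² = 4σ². Divided by 5, this adds 0.8σ² to the variance of the group means.

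**Step 2: what this does to the interval.** 600 simulated trials per scenario, fitted by REML without and with location as a fixed effect. Widths are mean 95% interval widths in SD units after baseline adjustment. The ratio is the width without location divided by the width with it.

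| Site share | Group ICC | Width without | Width with | Ratio | Group variance without | Group variance with |
|---|---|---|---|---|---|---|
| 0% | 0 | 1.058 | 1.102 | 0.960 | 0.043 | 0.051 |
| 0% | 5% | 1.088 | 1.134 | 0.959 | 0.075 | 0.084 |
| 2% | 0 | 1.061 | 1.086 | 0.977 | 0.047 | 0.045 |
| 2% | 5% | 1.111 | 1.124 | 0.988 | 0.094 | 0.087 |
| 5% | 0 | 1.080 | 1.073 | 1.007 | 0.065 | 0.049 |
| 5% | 5% | 1.131 | 1.116 | 1.013 | 0.108 | 0.085 |
| 10% | 0 | 1.128 | 1.052 | 1.072 | 0.107 | 0.052 |
| 10% | 5% | 1.153 | 1.090 | 1.058 | 0.135 | 0.085 |
| 20% | 0 | 1.187 | 0.989 | 1.200 | 0.161 | 0.041 |
| 20% | 5% | 1.214 | 1.019 | 1.191 | 0.195 | 0.070 |

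A separate simulation (2,000 trials per scenario, 82% retained, so about 7 × 0.82 = 5.7 per group and arm) gave:
- site 0, group 0: 1.059 / 1.092 = 0.970
- site 5%, group 5%: 1.149 / 1.117 = 1.029
- site 10%, group 0: 1.131 / 1.038 = 1.090

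**Step 3: standard error and coverage.** At site share 10% and group ICC 0, the empirical standard error of the arm difference is 0.220 with or without location. The mean model standard error is 0.260 without location (0.260 / 0.220 = 1.18) and 0.239 with it (0.239 / 0.220 = 1.09). Leaving location out does not make the estimate itself more variable; it only overstates its uncertainty. Some overstatement remains with location in, because the estimated group variance cannot fall below zero and averages 0.052 when the truth is 0. Coverage over all scenarios in the table is 96.3 to 98.5% without location and 96.2 to 97.8% with it.

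**Step 4: group variance.** The inflation without location, relative to the model with it, is:
- 5% site share: 0.108 / 0.085 = 1.27 to 0.065 / 0.049 = 1.33
- 10%: 0.135 / 0.085 = 1.59 to 0.107 / 0.052 = 2.06
- 20%: 0.195 / 0.070 = 2.79 to 0.161 / 0.041 = 3.93

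At 0 to 2% there is little or none.

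**The case against.** The best defence is that the protocol promises a full statistical analysis plan, never says that baseline is the sole covariate, and contradicts nothing if location is added later. That is fair as far as it goes. But the protocol did not leave the model open. It fixed the covariate, the clustering, the degrees of freedom and the fallback, and within that specification the stratification factor is missing.

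A reader might infer that the intervals and the clustering estimate *are* inflated. The documents do not support that. They give no between-site variance, and the direction changes with it: at 0 to 2% the planned interval is slightly narrower. A small residual share is possible, since all sites are in South West England, two are in Cornwall, everyone is screened into the same score bands, and baseline adjustment removes differences already present at entry. Sizeable differences are also possible, since different organisations deliver their own mapped programmes and the protocol itself stresses place-based inequality.

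A reader might also infer a biased effect or a damaged planned output. Neither follows. The estimate is unbiased and the error is conservative. The protocol lists standard deviations, not an ICC, as the quantity to carry forward. Six groups would give a poor ICC in any case.

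One caveat on the figures stands. Sample size and Power Calculations speaks of up to three courses per site and eight groups, while the randomisation section implies six. The simulations use six.

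**Conclusion.** The omission is real and the mechanism holds: the planned model does not reflect the stratified design, and residual site differences can widen the interval and inflate the group variance. The break-even lies between a site share of 2% and 5%, and the effect on interval width is material only from about 10%. These sizes rest on assumed site and group variances, six groups and balanced retention. The consequence is minor to moderate. The affected estimate is secondary and untested, and the primary objective (recruitment and retention) does not depend on this model. It is worth changing because the change is cheap, not because a result is known to be wrong.

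**What to change.** In Planned Data Analysis (Quantitative Data), extend the covariate sentence so that, after the baseline score, it adds: *and for location (three levels, fixed effect), the factor by which randomisation was stratified*. State that the ordinary-regression fallback uses the same terms. Carry both into the statistical analysis plan before data lock.

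The cost is one clause and two parameters drawn from few group-level degrees of freedom. With no site or group effect, the mean Satterthwaite degrees of freedom fall from about 16 to 12. Intervals are then about 3 to 4% wider (1.092 / 1.059 = 1.031; 1.102 / 1.058 = 1.042). No change to data collection or randomisation is needed.

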# **Objectives**

This pilot RCT and process evaluation (GREENGAGE) will provide information to design a definitive cluster RCT of nature-based activities in a group intervention format. As such it will:

- Measure recruitment rates at each site per month and inform optimisation of our models of recruitment.
- Measure rates of adherence during the intervention (percentage of participants attending at least four of the six (67%) nature-based activity sessions).
- Measure rates of loss to follow-up and data completeness
- Produce evidence to inform decisions regarding the primary outcome and primary endpoint for the definitive RCT.
- Estimate standard deviations of outcome measure to inform sample size calculation for the definitive RCT.
- Investigate the acceptability of being randomised to the intervention or wait list control groups to participants, and reasons for attrition.
- Explore the acceptability of proposed clinical and health economic measures to participants.

- Explore participants' experiences of the wider trial processes to refine these for the definitive trial.
- Explore the experiences of the nature-based providers of taking part in the pilot RCT.
- Understand the factors that support or challenge nature-based providers' ability to deliver the intervention in accordance with Handbook mechanisms.
- Develop a bid for a definitive RCT to be submitted to an appropriate funder (e.g. NIHR/MRC).
- Cost the intervention.
- Explore whether travel costs and/or residence in an area with relatively high social deprivation are correlated to participants' attendance
- Pilot data collection methods/instruments for resource use, health-related quality of life and well-being

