# **Data Management**

# **Quantitative Data**

Data will be recorded on the number of participants that are screened for participation and recruited to the pilot trial, further to their attendance of intervention participants at their NBSP intervention course, retention through the trial, and completion of the questionnaire data. Data on participant characteristics (age, gender, education level and postcode) will be collected at baseline. In addition, we will administer the five mental health and wellbeing measures, and the health service use questionnaire (see Appendix).

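### As written, travel cost is map distance priced at a mileage rate with no travel mode, so the cost–attendance objective would in effect be answered for distance

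*Protocol*

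**What the plan says.** The Objectives section of the protocol includes this item: "Explore whether travel costs and/or residence in an area with relatively high social deprivation are correlated to" attendance. The predictor named is cost, not distance.

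Planned Data Analysis, Quantitative Data, gives the method. Attendance is linked to postcode and the Index of Multiple Deprivation (IMD), and the question is whether travel costs and/or deprivation "is correlated to participant attendance using the Pearson correlation coefficient". Cost is built as follows: "Travel time and mileage from a participant's home postcode" to the site "will be calculated using Google Maps to incorporate participant travel costs, based on HMRC reimbursement rates". The web address given there is for mileage and fuel rates, which is vehicle-based pricing. The text does not state which rate applies, whether one rate applies to all, whether travel time is priced, or how a participant without a vehicle is costed.

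Under Data Management the protocol says: "Data on participant characteristics (age, gender, education level and postcode) will be collected at baseline". The data flow section lists age, gender, ethnicity, education and employment status. Neither list includes mode of travel or access to a car.

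The analysis section also describes a resource use questionnaire in which data collection for primary, secondary and social care use, "as well as personally incurred expenses (e.g. travel, counselling), informal care/support and workforce participation will also be piloted". Those travel expenses are not tied to the attendance correlation.

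**The concern.** A correlation coefficient does not change when a variable is multiplied by a positive constant. A cost made of mileage times a fixed rate therefore carries no information beyond mileage, and calling it cost does not make it one. For people who walk, use public transport or share a lift, the figure is also wrong as a cost. Travel time has the same gap, because it differs by mode and no mode is specified.

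This matters because the protocol's own background says that local transport influences uptake, and the inclusion section points to rural access problems and deprived wards near one site. A weak correlation could be read as showing that cost is no barrier, when the variable analysed was close to distance. If mode is never asked, no later analysis plan can recover it.

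**Working it through.** The plan states no figure on this point, so there is none to reproduce. All monetary, distance and mode inputs below are assumptions. The one input from the protocol is n = 42, the planned intervention arm.

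**1. One rate, time not priced.** Let cost = k × miles with k > 0. Then cov(k·miles, attendance) = k·cov(miles, attendance) and SD(k·miles) = k·SD(miles). The k cancels, so r(cost, attendance) = r(miles, attendance). In one simulated set of 42, r was −0.385 for distance and the same at rates of 0.20, 0.45 and 1.00 per mile (differences no larger than 2 × 10⁻¹⁶).

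**2. Time also priced.** In the same set, with 0.45 per mile plus 0.05, 0.10 or 0.20 per minute (return journey), r(cost, distance) was 0.999, 0.996 and 0.990. The correlation with attendance was −0.387, −0.387 and −0.386, against −0.385 for distance. The identity is no longer exact, but the result hardly moves.

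**3. Two rates.** If 10% or 30% of participants are priced at half the rate, the mean r(cost, distance) is about 0.96 or 0.90.

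**4. Non-drivers.** Assume gamma-distributed distances (shape 2, scale 5) and a driver's true cost of 0.9 per mile of one-way distance (0.45 × 2). Half the non-drivers pay nothing and half pay a flat fare of 4. Attendance (0 to 6 sessions) falls with true cost. Means over 3,000 sets of 42:

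| Non-drivers | r(imputed, true cost) | r(attendance, true cost) | r(attendance, imputed cost) |
|---|---|---|---|
| 0% | 1.00 | −0.39 | −0.39 |
| 10% | 0.89 | −0.40 | −0.36 |
| 20% | 0.79 | −0.40 | −0.32 |
| 30% | 0.69 | −0.38 | −0.27 |
| 50% | 0.52 | −0.37 | −0.20 |

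**5. Other cost models.** With non-drivers' costs drawn from 0, 4, 6 or 10, r(imputed, true) was about 0.80, 0.63 and 0.47 at 15%, 30% and 45% non-drivers. Multiplying by an assumed true correlation of −0.40 gives −0.40 × 0.80 = −0.32, −0.40 × 0.63 = −0.25 and −0.40 × 0.47 = −0.19. In the other direction, suppose non-drivers pay half the drivers' cost per mile, so that their cost rises with distance. The calculation is then that of step 3, and r(imputed, true) at 30% is about 0.90. At 30% non-drivers the three models therefore span roughly 0.63 to 0.90.

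**6. Precision.** For an observed r = −0.40 with n = 42, Fisher's z = −0.424 with standard error 1/√39 = 0.160. The 95% interval for z is −0.424 ± 0.314, that is −0.738 to −0.110, or about −0.63 to −0.11 for r. The attenuated values −0.32, −0.25 and −0.19 all lie inside it.

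**The case against.** Several points on the other side stand.

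- The protocol does not say that one rate is applied to everyone, and it calculates travel time as well as mileage. A reader might infer that the cost result is numerically identical to the distance result for all participants. That needs one rate and unpriced time, and neither is written.
- No separate correlation with distance is planned, so no analysis is duplicated. The issue is what the cost variable represents.
- A reader might infer that mode is not collected at all. The data collection tools are in an appendix that is not shown, and the two lists of baseline characteristics differ from each other, so neither is complete. What can be said is that no use of mode is stated.
- A reader might also infer that the pilot never measures cost. It pilots self-reported travel expenses. Moreover, a postcode-based figure exists for everyone, including people who never attend, which is a real merit of the planned approach.
- The attenuation figures rest on assumed inputs, and at n = 42 the pilot could not tell the attenuated values from −0.40.
- Barriers to attendance are also explored through surveys and focus groups.

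It can also be argued that rates and the handling of non-drivers belong in the analysis plan, which is not shown. That holds for the choice of rate. It does not hold for mode, which has to be collected from participants. Nor is this only an omission: the protocol states a costing rule, and followed as written that rule gives something close to distance.

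**Conclusion.** The point holds as a minor one. The protocol asks about travel cost and states a rule that yields essentially travel distance: exactly so for Pearson's r under one rate with time unpriced, and with a cost–distance correlation of about 0.90 to 0.999 in the assumed variants with priced time or two rates. For non-drivers the imputed figure is not their cost. The error grows with their share and with how far their true cost departs from distance, and the protocol gives neither.

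One might go further and say that the error is tied to deprivation, the other predictor, because people without cars are concentrated in deprived areas. That is plausible, but the protocol gives no figures on car access by deprivation, so it is not part of this conclusion. The objective is exploratory. The primary objective on recruitment and retention, the sample size and the outcome analyses are unaffected.

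**What to change.** Unless the questionnaires already ask it, add one item at T0 on how the participant would travel to the site: own vehicle, lift, public transport, or on foot or by cycle. T0 precedes randomisation, so the answer cannot be influenced by allocation or attendance.

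Revise the costing sentence in Planned Data Analysis so that, for every intervention-arm participant, the journey is costed and timed by the stated mode. State the rate or fare rule for each mode and whether time is priced. Report distance and cost as separate variables.

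Use the travel expenses already piloted in the resource use questionnaire only as a check among attenders, since people who never attend incur none. If mode cannot be collected, call the variable distance and interpret it as such.

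The cost is one extra question, one revised passage and modest work to price and time journeys by mode. The intended mode stated at T0 may differ from the mode actually used, so some misclassification would remain.
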